3.2.8 Embryo-Fetal Development Study in Rats

In the rat embryo-fetal development study, doses of LC9211 phosphate evaluated were 0, 1, 3, and 10 mg/kg/day. Test article-related non-adverse effects included decreased mean body weight and body weight gain (1, 3, and 10 mg/kg/day), decreased food consumption (3 and 10 mg/kg/day), reduced adjusted fetal weight parameters (10 mg/kg/day), and unossified phalanx hindlimb skeletal variations (10 mg/kg/day). No test article-related effects on maternal clinical or macroscopic observations, reproductive performance, or fetal external, visceral or skeletal malformations were noted. Based on the results of this study, the NOAEL for LX9211, administered as LX9211 phosphate by oral gavage to pregnant rats during the period of organogenesis, is 10 mg/kg/day. On Gestation Day 12 for this dose level, the C_{max} and AUC0-24 were 882 ng/mL and 12,000 ng*hr/mL, respectively, for LX9211.

3.2.9 Embryo-Fetal Development Study in Rabbits

In the rabbit embryo-fetal development study, doses of LX9211 phosphate evaluated were 0, 0.6, 2, and 4 mg/kg/day. No test article-related effects were noted on maternal body weight, food consumption, clinical or macroscopic observations, reproductive performance, cesarean section parameters, embryofetal toxicity, or fetal development. Based on the results of this study, the NOAEL for LX9211, administered as LX9211 phosphate by oral gavage to pregnant rabbits during the period of organogenesis, is 4 mg/kg/day. On Gestation Day 13 for this dose level, the C_{max} and AUC0-24 were 261 ng/mL and 4200 ng*hr/mL, respectively, for LX9211.

3.3 Clinical Trials of LX9211 in Humans

Three clinical studies have recently completed: LX9211.1-101-NRM, A Phase 1, Randomized, Double-blind, Placebo-controlled Ascending, Single-dose Study to Determine the Safety and Tolerability of Orally Administered LX9211 in Healthy Human Participants (SAD); LX9211.1-102-NRM, A Phase 1, Randomized, Double-blind, Placebo-controlled Ascending Multiple-dose Study to Determine the Safety and Tolerability and Pharmacokinetics of Orally Administered LX9211 in Healthy Volunteers (MAD); and LX9211.1-103-NRM, A Phase 1, Open-label, Nonrandomized, 2-part Study to Evaluate the Absorption, Metabolism, Excretion, Mass Balance, and Absolute Bioavailability of ¹⁴C-LX9211, Following Oral and Intravenous (IV) Administration in Healthy Male Subjects. A cohort of 6 male subjects were exposed to a single oral dose of ¹⁴C-LX9211 (nominal 50 mg free drug). Drug-related material in urine and feces was recovered for up to 34 days. The mean recovery percentage of drug-related material was 77.9%, with 48.7% collected in urine and 29.2% being collected in feces. There were no serious adverse events (SAEs) and the adverse events (AEs) experienced, were similar to those seen in the SAD and MAD studies; all were mild in severity.

In addition, a separate cohort of 6 subjects underwent an evaluation to establish the absolute oral bioavailability of LX9211. A single oral dose of 50 mg was administered, followed by an IV microdose (14 C-9211 50 µg). Again, there were no SAEs and the AEs experienced were similar to those seen in the SAD and MAD studies; all were mild in severity.

Both studies included females of nonchildbearing potential and males between the ages of 18 to 65 years. A total of 146 subjects were enrolled in the 2 studies, 112 of whom were randomized to receive LX9211.

The results from the LX9211-101 study showed that LX9211 was generally well tolerated in healthy normal subjects at single doses up to 300 mg. Results from cohorts exposed to single dose of LX9211 up to 300 mg are summarized as follows:

Adverse events were mild to moderate in intensity; there were no severe AEs, deaths, SAEs, or withdrawals due to AEs. The most common AEs were dizziness and headache. One subject in the 300 mg single-dose cohort experienced orthostatic tachycardia with an onset at 1-hour postdose and which lasted for 8 days. This event was reported by the Investigator as mild in intensity and related to study drug.

Systemic exposure to LX9211 (C_{max}, AUC₀₋₂₄, AUC₀₋₉₆, and AUC_{0-inf}) increased from 5 to 300 mg in an apparent dose-proportional manner when examined as the log functions of dose and

exposure. Median T_{max} of LX9211 was approximately 8-12 hours postdose and the mean $t_{1/2}$ ranged from 143 to 197 hours (6 to 8 days).

Based on the PK profile of LX9211 in the SAD study, subjects in the MAD study were given a loading dose on Day 1, followed by a daily maintenance dose on Days 2-14. This dosage regimen permitted steady state to be achieved quickly and then maintained for the duration of the study. Results from this study showed that LX9211 was well tolerated in healthy normal subjects receiving multiple doses (14 days) up to 200 mg loading dose. All AEs were mild in intensity; there were no severe AEs, deaths, or SAEs. One patient discontinued due to reported AEs: allergic rash, urticaria, and angioedema. All AEs were assessed as mild and resolved within a few days after being treated with a single oral dose of diphenhydramine. Overall, the AEs observed in the MAD study were similar to those reported in the SAD study. No clinically significant comprehensive metabolic panel (CMP), UA findings, or bladder dysfunction-related AEs were reported in any subject treated with LX9211 in the SAD or MAD studies with LX9211,

3.4 Rationale for Current Study

3.4.1 Rationale for Selection of Dose

The doses of LX9211 selected for evaluation in the current study were chosen based upon the safety, tolerability, and PK data observed from the prior single-dose and multiple-dose Phase 1 studies.

The doses studied in the SAD and MAD studies, in healthy volunteers, ranged from 5 to 300 mg. Single-dose administration demonstrated linear PK up to the highest tested dose (300 mg). There were no deaths, SAEs, discontinuations due to an AE, AEs of severe intensity, or any clinically significant laboratory, vital sign, physical exam (PE), or electrocardiogram (ECG) findings.

Multiple-dose administration demonstrated linear PK up to the highest tested dose (200 mg). There were no deaths, SAEs, discontinuations due to an AE, AEs of severe intensity, or any clinically significant laboratory, vital sign, PE, or ECG findings.

Based on the observed safety and tolerability data from single doses up to 300 mg and multiple doses up to 200 mg for 14 days, the dose levels selected in this study, 100 mg and 200 mg loading doses followed by 10 mg and 20 mg maintenance doses, respectively, are expected to be well tolerated and represent an adequate range for dose exploration.

3.5 Rationale for Study Design and Control Groups

The randomized, placebo-controlled, double-blind clinical design allows for unbiased comparison of efficacy and safety between 2 different dose levels of LX9211 and placebo. The treatment duration (6 weeks) selected for this study was chosen based on the expectation of seeing an efficacy signal for the doses of 100 mg and 200 mg, which were based on human safety and tolerability.

Use of a concurrent placebo control, randomization, and double-blind administration of study drug are intended to minimize bias. Implementation of an unblinded interim analysis will allow for a reestimated increase in the sample size if indicated by the interim results. The study is designed as a group sequential trial to accommodate the interim analysis, and to improve upon such a design, the interim analysis effect size result is used not only to possibly increase the sample size, but to provide guidance in early stopping for futility. The option of sample size reestimation (SSR) allows the study to maintain statistical power at the original specified value, and guard against its reduction due to an unexpected increase in the dropout rate or variability associated with the primary endpoint measure.

4. Study Objectives

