10.1 Determination of Sample Size

Proposed Sample Size

A sample size of 75 patients per treatment group who complete the 6-week double-blind Treatment Period will yield 80% power to detect a true mean difference of 1 unit between at least 1 of LX9211 treatment groups and placebo in ADPS change from Baseline, assuming a common standard deviation of 2 and an overall significance level of α=0.05 (2-sided Dunnett's test). Accounting for a dropout rate of 20%, a total of 282 patients (94 patients per treatment group) will be enrolled and randomly assigned to treatment in a 1:1:1 ratio. This sample size is adjusted for the multiple comparisons of each LX9211 treatment group with placebo (Westfall, 1999).

Sample Size Reestimation

Due to the uncertainty in the outcome for the primary endpoint analysis secondary to potential variations in some of the key design parameters such as the dropout rate and standard deviation associated with the targeted treatment group difference, an unblinded SSR adaptation will be implemented at the time of the interim analysis testing for futility. This will occur when the first 141 patients have been accrued and followed thru Week 6 or dropped out early from the trial (whichever event happens first). Should a patient drop out early in the study, but return for the Week 6 visit, the Week 6 data will be used in the analysis. The Chen-DeMets-Lan method will be used for the unblinded SSR since it requires minimal change from a group sequential test. This method requires specification for a number of criteria related to the allowable conditions for increasing the sample size that ensures that ordinary group sequential methods can be applied while seeing that the overall error is not inflated compared to the original group sequential design. The 2 primary conditions which are required and satisfied in the SSR for this study are that (a) the SSR is made at the penultimate look, and (b) the conditional power at the penultimate look occurs between 50% and 80.3% (the original specified power under the group sequential design). The SSR is linked to the projected effect size falling within this "promising" or "favorable" range of conditional power. Having satisfied these 2 main conditions, the Type I error rate after increasing the sample size until the conditional power equals the original target power will not be greater than the Type I error from the originally proposed design.

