To derive the reestimated number of patients at the interim analysis, a simulation will be made that inputs: the observed group mean difference and its common standard deviation, a value for

the maximum total number of patients (E[Max]) equal to 351 patients and, specification that the reestimation rule is the Exact E method. The Exact E method increases the patient number total until the desired conditional power is achieved.

nQuery Advisor Advanced Pro software (v8.5.2.0) (Statsols, Rathmaculling West, Cork, Ireland) was used to estimate the sample sizes.

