10.4.5.7 Interim Analysis

An interim analysis of the primary endpoint will be performed to test for futility when 50% of the planned information has been accrued. This will occur when the first 141 patients have been accrued and followed to endpoint at Week 6 or dropped out from the trial earlier, whichever event occurs first. Should a patient drop out early in the study, but return for the Week 6 visit, that Week 6 data will be used in the analysis.

A non-blinding futility boundary will be used to test treatment group differences in the primary endpoint at 50% of the original planned information. The set of boundary values will be derived by using a beta spending function and specification of a power family with value = 3.672. The monitoring boundary is constructed by assuming a 1-sided test with a per comparison Type I error rate = 0.0141, assuring an overall α = 0.025 (or a two-sided α = 0.05) for the two LX9211 versus placebo comparisons. Use of this beta spending function for futility testing is conservative and results in cumulative beta error rates of 0.015 and 0.197 at the interim and final analyses, respectively. Application of the futility analysis is to serve as a guideline and is not the only source of information used to evaluate the trial for a negative finding. Assessment of other data available at the interim analysis will be used to qualify the trial for a recommendation of futility (eg, secondary and other efficacy variables , safety data).

The futility analysis will be described in the SAP and DMC Charter documents.

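### The sample size reestimation gives only partial protection of power, not the maintained power claimed in Protocol 3.5; a minor point is that 0.0141 per comparison gives an overall alpha of 0.0261, not 0.025

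*Protocol*

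**What the plan says.** Protocol 3.5 gives the purpose of the reestimation: "The option of sample size reestimation (SSR) allows the study to maintain statistical power at the original specified value". It adds that this guards against loss of power from more dropout or a more variable primary endpoint than expected.

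The operating rules are in Protocol 10.1, repeated in SAP 2.3:

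- One condition for an increase is that "the conditional power at the penultimate look occurs between 50% and 80.3" percent, the upper figure being the original power of the group sequential design.
- The inputs are the observed group difference and SD, with a maximum of 351 patients.
- On how far N rises: "The Exact E method increases the patient number total until the desired conditional power is achieved".

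The planning assumptions are also in 10.1:

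- On size: "A sample size of 75 patients per treatment group who complete the 6-week double-blind Treatment Period will yield 80% power". The effect in question is a 1-unit advantage over placebo for one or both doses.
- On variability and alpha, the calculation is made "assuming a common standard deviation of 2 and an overall significance level of α=0.05 (2-sided Dunnett's test").
- On dropout: "Accounting for a dropout rate of 20%, a total of 282 patients (94 patients per treatment group") are to be randomized, and the interim look comes at the first 141.

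For the futility boundary, Protocol 10.4.5.7 and SAP 7.8 assume "a 1-sided test with a per comparison Type I error rate = 0.0141, assuring an overall" one-sided alpha of 0.025 across the two dose comparisons.

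**The concern.** A higher SD or more dropout lowers conditional power at the interim. It therefore moves more trials below the 50% floor, where no increase is allowed. Within the window, the cap of 351 often stops N short of the 80.3% target. A rule of this form cannot hold unconditional power at its original value against the threats that 3.5 names.

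Protecting power is the reason 3.5 gives for the SSR option. A reader who trusts that sentence would interpret a negative result as coming from a trial with about 80% power, when a modest overrun in SD would have left it near 70 to 78% for a single effective dose.

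Separately, the statement that 0.0141 per comparison secures an overall 0.025 can be checked directly from the 1:1:1 allocation.

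**Working it through.** **Inputs from the documents.** Difference 1, SD 2, 75 completers per arm, 20% dropout, N = 282, interim at 141 (information fraction t = 0.5), window 50% to 80.3%, cap 351, one-sided 0.0141 per comparison (c = 2.1945). The overruns in SD and dropout below are assumptions; the documents give only SD 2 and 20%.

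**1. Reproduce the plan's figures.** The drift is θ = 1/(2·√(2/75)) = 3.062. Power = Φ(3.062 − 2.1945) = 80.7% by the normal approximation, and 80.25% by the t distribution with 222 df. So 80.3% is reproduced as power for one comparison. The sample size follows from 75/(1 − 0.20) = 93.75, rounded to 94 per arm, or 282. Interim beta is 0.197 × 0.5^3.672 = 0.0155, against the stated 0.015.

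**2. The window on the z scale.** With r = N/282, conditional power at the observed trend is

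CP(z1; r) = Φ{[z1√t + (z1/√t)(r − t) − c√r] / √(r − t)}.

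At r = 1, CP = 50% at z1 = 1.552 and CP = 80.3% at z1 = 1.978.

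**3. What the cap delivers.** At the cap r = 351/282 = 1.2447. Starting from z1 = 1.552:

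- CP at 351 = Φ{[1.097 + 1.634 − 2.448]/0.863} = 62.9%.
- Reaching 80.3% would need about 498 patients.
- 351 is enough only if CP at 282 is already about 69.6%.

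The cap binds in about 58% of the trials that qualify for an increase.

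**4. Unconditional power for one effective dose.** Integrate over z1 ~ N(θ√t, 1), with r(z1) set by the rule and θ = 1/(SD·√(2/n)). Here n = 75, or 94(1 − d) for dropout d.

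| Scenario | Fixed 282 | With SSR |
|---|---|---|
| SD 2.0, 20% dropout | 80.7% | 82.0% |
| SD 2.1 | 76.5% | 77.9% |
| SD 2.2 | 72.2% | 73.7% |
| SD 2.3 | 68.0% | 69.6% |
| SD 2.0, 25% dropout | 78.1% | 79.4% |
| SD 2.0, 30% dropout | 75.0% | 76.4% |

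An increase is triggered in 15.6% of trials at SD 2.0 and 16.8% at SD 2.3; mean N is 290 to 291. CP is below 50%, so N stays at 282, in 27% of trials at SD 2.0 and 43% at SD 2.5. Power with SSR falls to 80.3% at SD 2.04 or at dropout of 23.5%.

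**5. Which rule limits the gain (SD 2.3).**

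- As written: 69.6%.
- Cap removed, window kept: 70.3%.
- Cap kept, 50% floor removed: about 76%.
- 351 enrolled in every trial: 78.1%.

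The window is the main limit and the cap the lesser one.

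**6. Overall alpha.** With equal allocation the two comparisons have correlation 0.5. Then P(max Z > 2.1945) = 0.0261 one-sided, or 0.0522 two-sided. An overall 0.025 needs z = 2.212, which is 0.0135 per comparison. Using 0.0135 moves power including futility from 80.5% to 80.1%, and the interim futility z from about 0.00 to 0.01.

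**The case against.** The best defence of 3.5 is that it is a rationale and is softly worded: SSR is an option that allows power to be kept, and the same paragraph says an increase is only possible. The window and the cap are both disclosed, and 10.1 ties the target to conditional rather than unconditional power. That softens the sentence but does not rescue it, because it names the quantity kept and the threats covered. The cap does stand directly before the stopping wording in 10.1 and SAP 2.3, so that correction is editorial.

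The figures also depend on how the rule is read. They assume one effective dose whose own comparison drives the SSR, and the documents do not say which dose drives it. In three-arm simulation the gain per comparison is 1.3 to 1.9 points if the better arm drives it and 1.3 to 2.8 points if any arm can. Mean N reaches about 299 in the latter case. If both doses work, power for at least one success is much higher, about 84% at SD 2.3. That comes mostly from having a second dose, and it is not the quantity that reproduces as 80.3%.

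Two smaller points stand. The dropout figures treat dropouts as giving no information, whereas the MMRM uses their earlier weeks and any Week 6 return visit, so that loss may be overstated. Using z = 2.212 instead of 2.194 moves the break-even SD from 2.04 to 2.03.

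On alpha, the objection that nothing in the final inference changes is correct. The 0.0141 builds only a non-binding futility guideline.

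**Conclusion.** The concern holds. Under the rules of 10.1 the SSR adds about 1.5 points of power for a single effective dose and keeps 80.3% only up to an SD about 2% above plan (2.04 against 2), or dropout of about 23%. This rests on conditional power at the observed effect, information proportional to completers, and power for one comparison. No reading of which arm drives the SSR raises the gain above 2.8 points. The window itself is sound: it is a condition of the cited method, and Type I error is not inflated (0.0139 per comparison with SSR, against 0.0141). What is wrong is the property claimed in 3.5.

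The alpha statement is also wrong as a number (0.0261, not 0.025). It is minor, since the Dunnett test at two-sided 0.05 governs the final comparisons.

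**What to change.** 1. In Protocol 3.5, replace the claim of maintained power with a statement that the SSR gives partial protection, because N rises only when interim conditional power is 50% to 80.3%, and only to 351. Add simulated power by SD and dropout. Say whether each figure is for one dose or for at least one, and which comparison drives the SSR.
2. In Protocol 10.1 and SAP 2.3, state that N rises until conditional power reaches 80.3% or N reaches 351, whichever comes first.
3. Minor: in Protocol 10.4.5.7 and SAP 7.8, replace 0.0141 with 0.0135 (z about 2.212). Rerun the design software for the futility boundary, the conditional power zone and the stated beta and power.

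The cost is wording in both documents and one software rerun. Stated power falls by about half a point. No extra patients are needed, and the final Dunnett test does not change.

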4.1 Primary Objective

• To evaluate the efficacy of LX9211 in reducing pain related to diabetic peripheral neuropathy (DPN)

4.2 Secondary Objective(s)

 To assess other effects and patient reported outcomes of LX9211 versus placebo following the 6-week double-blind Treatment Period

4.3 Other Objective(s)

- Change from Baseline in the Neuropathic Pain Symptom Inventory (NPSI) and to each week in the average daily pain score (ADPS), based on Question 5 of the Brief Pain Inventory DPN (BPI-DPN)
- To evaluate plasma C_{trough} levels of LX9211 at 2 oral dose levels in patients with type 1 diabetes mellitus (T1DM) and/or type 2 diabetes mellitus (T2DM) with chronic diabetic peripheral neuropathy pain (DPNP) over a 6-week period

The full PK profile of LX9211 will be evaluated in an optional substudy conducted in patients who consent to intensive PK sampling over the course of the treatment period.

Safety will be assessed by AEs, vital signs, ECG findings, and laboratory parameters.

5. Investigational Plan

5.1 Overall Study Design

This is a Phase 2, multicenter, randomized, double-blind, placebo-controlled, parallel-group study in patients with DPNP.

Scheduled study visits in the clinic will occur during Screening; at the initiation of the 2-week single-blind placebo Run-in Period; on Day 1 (Baseline) and during Weeks 2, 4, and 6 of the double-blind Treatment Period, and at Week 11 (Week 5 of the single-blind Safety Follow-up Period).

[figure not shown]
Male and female patients of nonchildbearing potential, age 18 years and above, diagnosed with T1DM or T2DM and with chronic DPNP, and who meet all inclusion and no exclusion criteria are eligible for enrollment.

Eligible patients may continue use of medications prescribed for DPNP including pregabalin, gabapentin, and antidepressant medications, as long as they have been at stable doses for at least 1 month prior to Screening and are willing to maintain their doses for the duration of the study. Use of any opioid medications for the management of DPNP within the 2 months prior to Screening is not permitted.

The treatment schema is summarized in Figure 5.1-1.

Figure 5.1–1 Treatment Schema

R = randomization EOT = end of treatment EW = early withdrawal

- ** Maintenance Dose (Day 2 Week 11 Visit)
- @ Day 1 may occur up to 2 weeks plus 3 days after start of the Run-In period

2 Optional Substudies:

- PK Evaluation and possible biomarker analysis (up to 30 patients) —
 Days 1 and 2, Week 2, Week 4, Week 6 or EOT/EW, Week 11 or 35 Days after
 EOT/EW
- Exit Phone Interview Within 2 to 3 weeks following the Week 6 Visit or EOT/EW

^{*-} Loading Dose (Day 1)

5.1.1 Screening Period

After signing the Informed Consent Form (ICF), all patients will enter a Screening Period of up to 2 weeks. Following confirmation of eligibility criteria, patients will enter the Run-in Period.

Note: Patients who fail Screening may be rescreened ONCE after discussion with the Medical Monitor. Patients who begin the Screening Period prior to this amendment and who otherwise would qualify for the study may be rescreened again so as to allow them to begin the Run-in Phase following implementation of this amendment.

